1 STUDY PURPOSE

The purpose of this Post Market Surveillance Validation is to document the performance and clinical outcomes of the MaxAn[®] Anterior Cervical Plate System. [name], et.al conducted a retrospective review and found a positive association between adjacent-level ossification following anterior cervical plate procedures and the plate-to-disc distance.¹ They concluded that when the anterior cervical plates were placed at least 5mm away from the adjacent disc spaces, there was a decrease in the likelihood of moderate-to-severe adjacent-level ossification. The design of the MaxAn Anterior Cervical Plate and accompanying technique allows this type of plate placement; therefore we will be looking at the radiographic outcomes of these subjects and comparing them to the retrospective chart review conducted by [name]. Using the MaxAn Technique allows you to achieve plate placement of 5mm from the supraadjacent level which will help minimize the risk of adjacent level ossification.

2 PRODUCT DESCRIPTION

Device Name: MaxAn[®] Anterior Cervical Plate System

The MaxAn[®] Anterior Cervical Plate System provides a simple, efficient and innovative approach to anterior cervical plating. The system offers a decompression-based technique for cervical spine stabilization and introduces an innovative one-level plate technique that provides a direct relationship between the bone graft/spacer size and the position of the plate holes. The unique ability to obtain maximum screw angulation and place a fixed screw at any angle up to 30° cephalad on the superior end of the plate and up to 30°caudal on the inferior end of the plate allows for versatile screw placement close to the endplates. Note that the screws converge at 10° in the transverse plane and are not intended to have additional variability in that plane. The significant cephalad-caudal angulation affords the surgeon the opportunity to choose a smaller plate to help minimize the potential for adjacent level ossification.

The plate is low profile and allows for excellent intra-operative visualization of the vertebral end plate and graft. The system also provides a choice of fixed and variable self-drilling screws to provide the surgeon with multiple options.

The MaxAn[®] Anterior Cervical Plate System is an anterior cervical spinal fixation device made from titanium alloy (Ti-6Al-4VELI). Pre-contoured plates that conform to the natural lordotic curvature of the spine are available in one, two, or three level configurations. These offerings also range from 8.0mm to 72mm in length when measured from screw hole to screw hole. The system includes variable and fixed bone screws, which are available in 4.0mm and 4.5mm diameters in various lengths. The MaxAn[®] Anterior Cervical Plate System is cleared under K080646.

Indications For Use: The MaxAn[®] Anterior Cervical Plate System is intended for anterior interbody screw fixation of the cervical spine. The system is indicated for use in the temporary stabilization of the anterior spine during the development of cervical spinal fusions in patients with degenerative disc disease (as defined by neck pain of discogenic origin confirmed by patient history and radiographic studies), trauma (including fractures), tumors, deformity (defined as 'kyphosis, lordosis, or scoliosis), pseudarthrosis, and/or failed previous fusions. The intended levels for treatment range from C2 -T1.

Contraindications for Use: The MaxAn[®] Anterior Cervical Plate System is contraindicated in patients with spinal infection or inflammation; morbid obesity; mental illness, alcoholism or drug abuse; pregnancy; metal sensitivity/foreign body sensitivity; inadequate tissue coverage over the operative site, open wounds local to the operative area, or rapid joint disease, bone absorption, osteopenia and/or osteoporosis. Osteoporosis is a relative contraindication since the condition may limit the degree of obtainable correction, the amount of mechanical fixation and/or intolerance.

3 STUDY DESIGN

This post market surveillance study will enroll up to two hundred (200) subjects at up to 15 clinical centers within the United States with subjects followed for 24 months post-surgery. All subjects enrolled in the study will be recruited from the pool of subjects presenting to each investigational site for an anterior cervical fusion procedure. The up to 15 surgeons chosen to participate in this study will be thoroughly knowledgeable in the medical, surgical and mechanical aspects of the MaxAn[®] Anterior Cervical Plate System. The following inclusion and exclusion criteria must be met for a patient to be considered eligible for participation in this study.

3.1 Inclusion Criteria

- Subject is scheduled to undergo a one to three-level primary spinal fusion surgery between the levels of C2-T1 (Cervical 2 to Thoracic 1) using the MaxAn[®] Anterior Cervical Plate System.
- Subject has agreed to participate in this study, sign the informed consent and have agreed to return for the 6, 12 and 24 month follow-up visits.
- Subjects or their representative must be willing and able to give informed consent.

3.2 Exclusion Criteria

- Subject has spinal infection or inflammation at any level.
- Subject is morbidly obese, defined as a BMI greater than 40.
- Subject has a mental illness, alcoholism or drug abuse.
- Subject has a metal sensitivity/foreign body sensitivity.
- Subject has inadequate tissue coverage over the operative site.
- Subject has an open wound local to the operative area, or rapid joint disease, bone absorption, osteopenia and/or osteoporosis.
- Female subjects who are pregnant or plan to become pregnant in the next 24 months or who are lactating.
- Subject who does not meet the specific indications for use of the MaxAn[®] Anterior Cervical Plate System.
- Subjects participating in another clinical research study.
- Any previous cervical spinal surgery.

4 STUDY PROCEDURES

All subjects who have agreed to participate in this study, have signed the informed consent and who meet the inclusion / exclusion criteria will be considered enrolled and assigned a subject ID number. Once a Subject ID number has been issued, it can not be reassigned or used for another subject.

Subjects will be followed pre-operatively, intra-operatively and postoperatively at 6, 12 and 24 months. The following data will be recorded on the Case Report Forms (CRFs) and in addition, electronic data entry will be employed via an Internet connection when possible using an Electronic Data Capture (EDC) program.

The subject number will be assigned to the subject as they are enrolled in the subject and be recorded in the study binder, which will remain at the clinical site. The monitors will only have access to the Subject Number Assignment List while they are at a clinical site reviewing the data.

4.1 Pre-Operative Assessment

4.1.1 Consent

All subjects over the age of 18 will be provided with an informed consent form and will be given ample time to review, ask questions, and sign the document. All subjects who meet all of the entry criteria will be considered for inclusion in this study. All subjects meeting any one of the exclusion criteria will be excluded from the study.

4.1.2 Medical History

Within 60 days prior to the surgery date, the following information will be collected according to the parameters described by the MaxAn Post Market CRFs:

- Demographics
- Medical history, including a complete history of spinal disorder(s) (non-operative or operative treatments performed)
- Physical examination (including height, weight)
- X-Rays
- Current pain medications and other drug therapies.
- Pain/Function Disability Assessment (Neck Disability Index (NDI) form).
- Health Assessment SF-36
- Neck and Shoulder/Arm Visual Analog Scale (VAS)

4.1.3 Clinical Assessment

The subject will undergo the following pain and function assessments within 60 days prior to the surgery date:

Pain/Function Disability Assessment: Pre-operatively the subject will complete the Neck Disability Index Questionnaire. The questionnaire is a combined pain and function index. It will be used to assess the subject's neck pain and how that pain affects the subject's ability to manage in everyday life.

The questionnaire is divided into ten sections designed to assess limitations of various activities of daily living. Each section contains six statements and each statement describes a greater degree of difficulty in that activity than the preceding statement. The subject marks the one statement in each section, which describes his/her limitations most accurately. Each section is scored on a 0-5 scale, 5 representing the greatest disability. The scores for all sections are added together, giving a possible score of 50. The total is doubled and expressed as a percentage. If a subject marks two statements, the highest scoring statement is recorded as a true indication of his disability. If a section is not completed because it is inapplicable, the final score is adjusted to obtain a percentage.

Neck and Shoulder/Arm Pain: Preoperatively all subjects will assess their neck and/or radicular shoulder/Arm pain in one or both arms using a visual analogue scale (VAS) from 0-100 mm with 100 being considered most painful.

SF-36v2[™] Health Survey: Preoperatively all subjects will complete a SF-36v2[™] Health Survey as an outcome measure to assess quality of life.

4.2 Perioperative and Postoperative Management

The Surgeon will perform a 1 to 3 level anterior cervical discectomy and fusion per their usual technique. Patient positioning and exposure will be performed by the surgeon as per their usual technique in accordance with the current published MaxAn Anterior Cervical Plate System Surgical Technique. The surgeon will also take care to perform the discectomy(ies) and endplate preparation(s) to their liking and will insert the graft(s) of their choosing per their preferred insertion method. On label indications include use of: machined allograft spacers, with or without bone graft extenders or interbody fusion devices with autogenous bone, with or without bone graft extenders. This study protocol stipulates that screw hole placement will be specific to the MaxAn Anterior Cervical Plate System technique in which screw holes are placed within 1.5mm of the cephalad treated endplate. This helps to enable the hardware to be greater than 5mm from the supradjacent level. Screw hole placement and preparation will be done via one of the following methods for this study:

1. Using the MaxAn System Trial Drill Guide which pre-drills screw holes 1.5mm above and below the endplates in a one level construct and drills the cephalad holes 1.5mm above the endplate in a two or three level construct
2. Using the MaxAn System Endplate Drill Guide which pre-drills the cephalad screw holes 1.5mm above the endplate in a two or three level construct

3. Using the MaxAn Single or Double Barrel Drill Guide which requires that the surgeon take care to place the screw holes within 1.5mm of the cephalad endplate
4. Using no MaxAn drill guide while "free handing" the screws into the plate, requiring the surgeon to take care to place the holes within 1.5mm of the cephalad treated endplate
5. Using no MaxAn drill guide while placing the Punch Awl, requiring the surgeon take care to place the punch awl pilot within 1.5mm of the cephalad treated endplate

Screws will be locked and tightened per the MaxAn System ring locking mechanism and closure will be performed per the surgeon's normal preference in an ACDF. Data will be collected during and immediately after the surgery according to the parameters described by the MaxAn[®] Anterior Cervical Plate CRFs. This includes: duration of surgery, blood loss, OR time, length of hospital stay, instrumentation used, type of procedure, surgical level, biological augmentation, type of implants and any interbody fixation system used (if applicable). In addition, all intra-operative complications (e.g. excessive blood loss, hematoma, vascular injury, etc.) will be reported and recorded as a complication on the CRF.

Intra-operative (after hardware is completed) or immediate post-operative x-rays need to be obtained at this time point. These images will be provided to Biomet to review along with the data collected from the surgical visit. We will be assessing the position of the plate at this time point at both the plate level and the distance to the adjacent level. Postoperative care will follow the standard of care at each institution for subjects who undergo anterior cervical fusion procedures.

4.3 Follow-up Assessment

Subjects will be asked to return postoperatively at 6 (\pm 2weeks), 12 (\pm 1 month) and 24 (\pm 1 month) months for a clinical and radiographic exam. Data collected during this exam will include:

- Clinical assessment: The investigator will carry out a clinical examination at the 6, 12 and 24 month visit to assess:
 - subject compliance with postoperative care instructions,
 - ability to return to work and normal activity, and

- any procedure related or device related adverse events since discharge from the hospital
- Subject self-assessment:
 - Each subject will be asked to complete a follow-up Neck Disability Index (NDI) form, SF-36 form and a Neck and Shoulder/Arm Pain VAS form at each follow-up visit.
- Radiographic assessment: Each subject will undergo AP, lateral and flexion extension x-rays at the 6, 12 and 24 month visit to assess:
 - Presence / absence of heterotopic bone at the fusion site or at adjacent vertebral levels
 - integrity of the device, with observation for events such as plate and/or spacer migration or subsidence, hardware fracture, and progress towards fusion consolidation

Findings from any additional imaging studies deemed necessary by the investigator will be recorded and reported with study results.

Published data from the current literature will be gathered for purposes of comparing operating room time and the surgeon's assessment of fusion compared with that reported in this study.

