5 COMPLICATIONS

In addition to the standard operating procedures for reporting complications per hospital/physician protocol, all clinical events, including both observed or volunteered problems, complaints, symptoms, physical signs or disease which either occur during the study, having been absent at baseline, or, if present at baseline, appear to worsen during the clinical outcomes collection study are to be recorded as complications in the subject's medical record and on the appropriate case report form. In addition for any cleared device, a Product Experience Report (PER) must be completed per the manufacturer's customary complaint procedure (SOP 114.0.1 – Product Complaint Procedure).

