APPENDIX 1: Data Collection Forms

The designated protocol visits occur pre-operatively, intra- and post-operatively and 3-months post-operatively.

Informed Consent Form – Signed by subject at pre-op visit.
Demographics & Physical Exam – Completed by STAFF, information found in Medical History. This form is completed only once.
Medical History - Completed by STAFF, information found in Medical History. This form is completed only once.
Previous Spine Surgery History - Completed by STAFF. This form is completed only once.
Non-Operative Treatment - Completed by STAFF. This form is completed only once.
Current Surgery - Completed by STAFF, information taken from Operative Notes and Discharge Report. This form is completed only once after the subject has had surgery.
Post Market Follow-Up Survey – to be completed by operating SURGEON at the 6, 12 and 24 month follow-up visits.
Neck Disability Index Form – To be completed by the subject at the pre-operative and 6, 12 and 24 month follow-up visits.
SF-36 Health Survey – To be completed by the subject at the pre-operative and 6, 12 and 24 month follow-up visits.
Neck and Shoulder/Arm Pain VAS – To be completed by the subject at the pre-operative and 6, 12 and 24 month follow-up visits.
Medication Log - Completed by STAFF. This form is completed and updated pre-operatively, intra-operatively, post-operatively, and at the 6, 12 and 24-month follow-up visits.
Complications Form - Completed by STAFF or SURGEON only if this occurs.

BTBS.CR.SP.009.11v1

MaxAn[®] Cervical Post Market Surveillance

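### Sections 4.2, 4.3, 5 and 5.1 set different scopes for recording complications, and no section states a prompt for events judged unrelated or for events between wound closure and discharge

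*Combined protocol and SAP*

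**What the plan says.** Four parts of the combined protocol and SAP bear on which events are recorded.

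- **Section 5, opening paragraph.** It covers "all clinical events, including both observed or volunteered problems, complaints, symptoms, physical signs or disease which either occur during the study", if absent at baseline. Conditions already there at baseline count as well if they seem to get worse, and every such event goes both in the medical record and on the CRF. There is no relatedness condition and no start at discharge. The duty is an addition to local reporting: "In addition to the standard operating procedures for reporting complications per hospital/physician protocol".
- **Section 4.3.** Among the items for the clinical examination at 6, 12 and 24 months is "any procedure related or device related adverse events since discharge from the hospital".
- **Section 4.2.** For the operation, "all intra-operative complications (e.g. excessive blood loss, hematoma, vascular injury, etc.) will be reported and recorded as a complication on the CRF".
- **Section 5.1.** Under the heading for the definition, a complication is a communication alleging a deficiency of the device, its labeling or its packaging. The text itself goes on to call this a complaint.

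Appendix 1 lists the forms. The entry for events reads "Complications Form - Completed by STAFF or SURGEON only if this occurs". The Post Market Follow-Up Survey is completed by the operating surgeon at each follow-up visit. The forms themselves are not reproduced.

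**The concern.** Section 1 gives the purpose as documenting the performance and clinical outcomes of the plate, and Section 4.5 says results will be reported in tables and descriptive statistics. A descriptive complication count is only as good as the rule for collecting it. Here the rule depends on which section a site works from.

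A visit run to Section 4.3 assesses a subset of what Section 5 requires. Relatedness then acts as a condition for recording an event, when it should be a property noted once the event is recorded. The judgement falls to the investigator at a visit whose survey is completed by the surgeon who operated. An event on the ward after closure and before discharge is named neither in 4.2, which stops at the operation, nor in 4.3, which starts at discharge. At stake are under-recording of complications and differences between up to 15 centers that reflect reading habits rather than outcomes.

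**Working it through.** No arithmetic decides this point, so the rules are set side by side.

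| Source | Which events | Period | Relatedness needed? |
|---|---|---|---|
| Section 5, opening | all new or worsened clinical events | whole study | no |
| Section 4.3 | adverse events | from discharge, at 6, 12 and 24 months | yes, procedure or device |
| Section 4.2 | intra-operative complications | the operation | no |
| Section 5.1 | communications alleging device deficiencies | after release of the product | device only |

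**Step 1: event judged unrelated, after discharge.** Section 5 requires it on the form. The item in 4.3 does not reach it, and no other visit text asks for it.

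**Step 2: event between closure and discharge.** Section 5 requires it. The complication sentence in 4.2 does not name it, and the window in 4.3 has not opened.

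**Step 3: other routes for the same information.**
- Section 4.2 also states "Data will be collected during and immediately after the surgery according to the parameters described by the MaxAn" forms, and it lists length of stay.
- The Current Surgery form in Appendix 1 is "Completed by STAFF, information taken from Operative Notes and Discharge Report", so the record of the index stay is read.
- The Medication Log is updated post-operatively and at each visit.
- Section 7.8 has monitors check the forms for completeness against source documents, which under Section 7.5 include hospital and clinic records.
- Section 7.8.1 has incoming data reviewed for adverse events, with no relatedness limit.

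Each route may bring an event to light. None of them is a stated question about complications in the two gaps.

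**Step 4: what Section 5.1 adds.** A site looking up the headed definition finds a third scope, limited to alleged product deficiencies. Citing Section 5 as a whole would therefore not settle which scope applies.

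**Step 5: does it reach the primary endpoint?** Section 6 uses the 24-month lateral radiograph, and Section 4.4 places the grading in an independent review. The plan's only sample-size calculation reproduces: 1.96² × 0.455 × 0.545 / 0.10² = 95.26, rounded up to 96; 96 / 0.85 = 112.94, rounded up to 113. No complication rate enters it, so neither the endpoint nor the sample size changes.

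**The case against.** The strongest reply is that the texts can all be obeyed at once. The list in 4.3 is introduced as what the data will include, so it is not exclusive, and nothing in it forbids recording other events. Section 5 already makes recording mandatory throughout, in both the medical record and the case report form. A ward hematoma has to be recorded whether or not 4.2 names it. Staff as well as the surgeon may complete the Complications Form, so the surgeon is not the only route. The routes in Step 3 add further cover.

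Much of this stands, and it rules out several stronger readings that a reader might infer.

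- *Unrelated events and pre-discharge events are never actively sought.* Not supported: the general duty applies to both, the Discharge Report is read, and the forms cannot be inspected. The supportable statement is that no section states an explicit prompt.
- *Adjacent-level problems attributed to natural progression are lost.* Not supported: NDI, SF-36 and the neck and arm VAS are collected at every follow-up visit whatever the attribution, and adjacent levels are assessed radiographically. What may be missed is the record of the event as a complication.
- *A missing Complications Form cannot tell no event from not asked.* This holds for the listed text only. The Post Market Follow-Up Survey may already contain such a question.

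The reply does not remove the mismatch. Section 5 sets the duty, but the visit instruction meant to carry it out is narrower, and the definition in 5.1 points elsewhere. The backstops are indirect: a medication change or an NDI score is not an event record, and central review sees only what sites submit.

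**Conclusion.** The point holds as a mismatch of scope between four sections, worth correcting because complication counts are part of what the study is meant to document. The expected direction is under-recording relative to the opening paragraph of Section 5, possibly to different degrees between sites.

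The size cannot be estimated from the documents. A reader might attempt recorded rate = r × (1 − u), where r is the true event rate and u the share judged unrelated. With r assumed at 15% and u at 20% to 50%, this gives 0.15 × 0.80 = 12.0% down to 0.15 × 0.50 = 7.5%. Neither input is in the documents, and the formula supposes that sites ignore Section 5 and that every backstop fails. It shows the direction only.

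The conclusion rests on two conditions: that at least some sites take 4.3 as their working instruction, and that the forms do not already carry a broader prompt. The first is plausible but not shown; the second can be checked by the sponsor from the forms. The primary radiographic endpoint is unaffected.

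**What to change.** - **Section 4.3:** replace the adverse-event item with: *all new or worsened clinical events, as described in the opening paragraph of Section 5, since surgery (first visit) or since the last visit (later visits)*. The reference must be to the opening paragraph, because a reference to Section 5 as a whole could bring in the complaint definition of 5.1.
- **Section 4.2:** extend the complication sentence to cover complications from the start of surgery to discharge.
- **Relatedness:** record relationship to device and to procedure as attributes of each event once it is on the form, not as a condition for recording it.
- **Section 5.1:** relabel the text as the definition of a product complaint, so that it no longer governs complication recording.
- **Post Market Follow-Up Survey:** check the form. If it has no such item, add one yes/no question on any complication since surgery or the last visit, so that an absent Complications Form can be read as no event.

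Cost: wording in three sections, one attribute per event, and at most one new item on an existing form, with no new visits. The downside is slightly more abstraction at existing visits and a somewhat higher reported complication count.

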4.4 Independent Radiologist Assessment

An independent radiographic analysis will be performed to evaluate all images and assess subjects' radiographic status. The following quantitative and qualitative assessments will be performed.

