4.4.6 Fusion Determination

Fusion will be assessed by an independent radiographer when data collection is complete at each site. The radiographic report (if available) and the x-rays will be sent to an independent radiologist for review at the end of the study. X-rays will be evaluated at each visit for fusion determination. The grading system is as follows:

- Grade 1 - No graft incorporation
- Grade 2 - Incomplete graft incorporation
- Grade 3 - Graft Incorporation
- Grade 4 - Solid fusion with graft incorporation

Radiographic Success: Radiographic success is defined by graft incorporation or solid fusion with graft incorporation (Grade 3 or 4)

Radiographic Failure: Radiographic failure is defined by incomplete graft incorporation or no graft incorporation (Grade 1 or 2).

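### The fusion comparison with published data names the surgeon's reading, with no scale, threshold or visit stated there, although an independent graded read is already planned

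*Combined protocol and SAP*

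**What the plan says.** The closing sentence of Section 4.3 (Follow-up Assessment) begins "Published data from the current literature will be gathered for purposes of" and continues "comparing operating room time and the surgeon's assessment of fusion compared with that reported in this study". No other fusion measure is named for that comparison, and no published source for fusion is identified.

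On the films, Section 4.3 states: "Each subject will undergo AP, lateral and flexion extension x-rays at the 6, 12 and 24 month visit to assess" a list of findings that includes progress towards fusion. The list gives no grades and no rule for calling a level fused. Appendix 1 has a Post Market Follow-Up Survey that is "to be completed by operating SURGEON at the 6, 12 and 24 month follow-up visits"; its items are not shown.

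Section 4.4 then plans a separate evaluation: "An independent radiographic analysis will be performed to evaluate all images and assess subjects' radiographic status". Section 4.4.6 adds: "Fusion will be assessed by an independent radiographer when data collection is complete at each site", and also "X-rays will be evaluated at each visit for fusion determination". It sets out four grades, with Grades 3 and 4 as radiographic success and Grades 1 and 2 as failure. Section 4.5 says that outcomes will be reported with tables and descriptive statistics.

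**The concern.** The plan defines one fusion outcome carefully and names a different, undefined one for its external comparison. This is a single-arm study, so a difference in who reads the films does not cancel between arms. It becomes part of the difference from the literature. A surgeon taking part in the study knows the device and has an interest in the result. With up to 15 surgeons (Section 3) and no threshold stated in Section 4.3, the reading may also vary between sites.

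At stake is the credibility of the statement the study will make about fusion, which is central to the plate's indication in Section 2. Enrolling more subjects would narrow the interval but would not reduce a reading bias.

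**Working it through.** **1. The plan's own figure.** Section 6 gives no figure for fusion; its sample size concerns adjacent-level ossification. Inputs: rate 45.5%, precision 10 points, two-sided 95% confidence, attrition 15%.

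- n = 1.96² × 0.455 × 0.545 / 0.10² = 95.26, rounded up to 96.
- 96 / 0.85 = 112.9, rounded up to 113.

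Both stated figures reproduce. Neither depends on which fusion reading is compared with the literature.

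**2. The two fusion readings side by side.**

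| | Surgeon (Section 4.3) | Independent reader (Sections 4.4 and 4.4.6) |
|---|---|---|
| Scale | none stated there | four grades |
| Success rule | none stated there | Grade 3 or 4 |
| Visit | none named for the comparison | every visit read; none singled out |
| Independent of the treating team | no | yes |
| Named for the literature comparison | yes | no |

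**3. Possible size (illustration).** The documents give neither a fusion rate nor any disagreement between readers, so both inputs are assumed: a true fusion rate f of 80% to 95%, and a share x of 10% to 50% of non-fused cases that the surgeon reads as fused, with no errors the other way. Errors the other way would offset the bias.

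- Bias = x × (1 − f).
- 95% half-width = 1.96 × √(f(1 − f)/n), with n = 96 borrowed from Section 6.

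| f | Bias, x = 10% | Bias, x = 25% | Bias, x = 50% | Half-width, n = 96 |
|---|---|---|---|---|
| 80% | 2.0 | 5.0 | 10.0 | 8.0 |
| 85% | 1.5 | 3.75 | 7.5 | 7.1 |
| 90% | 1.0 | 2.5 | 5.0 | 6.0 |
| 95% | 0.5 | 1.25 | 2.5 | 4.4 |

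All bias and half-width entries are percentage points. The bias exceeds the half-width in 2 of the 12 combinations, both with half of the non-fusions misread. If the ceiling of 200 subjects in Section 3 were enrolled with 15% attrition (200 × 0.85 = 170), the half-widths would fall to 6.0, 5.4, 4.5 and 3.3 points while the bias stayed the same, and it would exceed the half-width in 3 of the 12.

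**4. What a larger shift would require.** At a true rate of 90%, a 5-point inflation needs 5/10 = half of all non-fusions to be misread, and a 10-point inflation needs 10/10 = all of them. If 90% is instead the surgeon-read rate, the true rates are 85% and 80%, and the shares are 5/15 = 33% and 10/20 = 50%.

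**The case against.** The strongest defence is comparability. If the published rates were read by the treating surgeons, a surgeon-read study rate is the like-for-like figure, and an independent rate would create a mismatch of its own. That stands, and it is why the surgeon's reading should be kept rather than dropped. It does not justify the present text: no fusion source is named, and a surgeon reading with no stated rule cannot be shown to match anything.

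The sentence in Section 4.3 is also loosely built. The surgeon's reading could be taken to describe the published side only. That is the less natural reading, and it would call for the same clarification.

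A reader might go further in three ways that the documents do not support:

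- That the independent read goes unused. Section 4.4.6 defines success and failure on it, and Section 4.5 provides for reporting outcomes; it is only not named for this comparison.
- That both readings are already in hand. The independent read is planned for late in the study. No form shown lists a surgeon fusion item. That the assessor is the operating surgeon is inferred from the survey in Appendix 1.
- That the surgeon has no scale at all. One could sit on a case report form whose content is not shown; it is only absent from Section 4.3.

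**Conclusion.** The point holds as a weakness in the choice of measure for a secondary, descriptive comparison. The plan names a reading open to assessor bias, with no stated definition, where a defined independent one is available at no extra cost in films or visits.

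The direction of bias is plausibly upward, but this is not demonstrated. A reader might infer that the fusion rate will be overstated by 5 to 10 points. The documents do not support that: they contain no disagreement data, and shifts of that size need a third or more of non-fusions to be misread under the assumptions above. What can be said is that the bias may be negligible or comparable to sampling error, which is about 4 to 8 points at 96 subjects for assumed rates of 95% to 80%.

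The primary ossification estimate and the 96/113 sample size are not affected.

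**What to change.** Amend the last sentence of Section 4.3 to:

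- make the independent Grade 3/4 success rate of Section 4.4.6, at a named visit, the main fusion result in the literature comparison;
- show the surgeon's assessment beside it, where recorded, with a cross-tabulation of the two readings to report agreement;
- record for each published rate who read the films and how fusion was defined, and compare surgeon-read sources with the surgeon-read rate.

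The cost is a sentence or two, settled before results are known, with no new films, readers or subjects. There are two downsides. The headline fusion rate may be slightly less favourable. For surgeon-read published rates the independent figure is not like-for-like, which is why the surgeon-read comparison stays for those sources. If the case report forms hold no surgeon fusion item, the surgeon-read comparison cannot be made, and Section 4.3 should say so.
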